2.5.1.2 Dose changes

All doses of the study drugs along with reasons for any dose change will be listed.

Dose interruption: Any dose interruption flagged in the DAR CRF page with a reason other than "as per protocol". Actual dose equal to zero between the first and last non-zero doses, following a non-zero actual dose.

Dose reduction: Any dose change flagged in the DAR CRF page with a reason other than "as per protocol". A non-zero actual dose that is less than the immediate previous non-zero actual dose (if not the first dose) and below the treatment planned dose.

Frequency counts and percentages of patients who have dose reductions or interruptions, and the corresponding reasons, will be provided for each study drug. The number of dose interruptions per patient, and the duration of dose interruptions (days) will be summarized for each study drug. Also, the number of dose reductions per patient and the duration of dose reductions (days) will be summarized for each study drug and treatment group.

2.5.2 Prior and Concomitant therapies

Concomitant therapies are defined as any medications (excluding study treatment, prior antineoplastic treatments) and significant non-drug therapies (including physical therapy and blood transfusions) administered in the study and are recorded in the Concomitant Medications/significant non-drug therapies eCRF. These therapies will be coded using the WHO Drug Reference Listing (WHO DRL) dictionary that employs the WHO Anatomical Therapeutic Chemical (WHO ATC) classification system.

Concomitant therapy and significant non-drug therapies prior to or after the start of the study drug will be listed by patient.

The imputation of a concomitant medication start date will follow the same conventions as for an AE start date (see [Section 2.8.1](#)). No imputation will be performed for concomitant medication end dates.

2.5.3 Compliance

Compliance is presented as the percentage of patients who took a predefined percentage (RDI categories: <0.5, 0.5-<0.75, 0.75- <0.9, 0.9-<1.1, ≥1.1) of the number of prescribed doses of study treatment. Details have been provided in [Section 2.5.1.1](#).

2.6 Analysis of the primary variable(s)

2.6.1 Phase I: dose escalation part

For the single agent LAG525 dose escalation arm, the primary variable is the incidence of DLTs in the first cycle of treatment. For the combo dose escalation arm, the primary variable is the incidence of DLTs in the first two cycles of treatment.

An adaptive BLRM guided by the Escalation with overdose control (EWOC) principle ([Babb et al 1998](#)) will be used to make dose recommendations and estimate the MTD(s)/RP2D(s) during the escalation parts of the study using DDS set. The methodology is described in detail in [[CLAG525X2101C Amendment 10 Section 10.4.2](#)].

In the single-agent LAG525 dose escalation part, the dose-toxicity (DLT) relationship is described by the following 2-parameter BLRM:

$$\text{logit}(\pi_1(d_1)) = \log(\alpha_1) + \beta_1 \log(d_1/d_1^*), \quad \alpha_1 > 0, \beta_1 > 0$$

where $\text{logit}(\pi_1(d_1)) = \log(\pi_1(d_1)/(1-\pi_1(d_1)))$, and $\pi_1(d_1)$ is the probability of a DLT at dose d_1 , where d_1 represents the Q2Wdose of LAG525. Doses are rescaled as d_1/d_1^* with reference dose $d_1^*=3$ mg/kg of LAG525. As a consequence α_1 is equal to the odds of DLT rate at d_1^* . Note that for a dose equal to zero, the probability of toxicity is zero.

For Japanese patients, the same model as above will be applied to guide single agent dose escalation decisions. Currently available information about the dose-DLT relationships of single agent LAG525 in Arm A will be used to derive informative priors for the BLRM parameters describing the dose-DLT relationships of this agent taking into consideration the heterogeneity between the global population and Japanese patients. For further details on the statistical model including the prior specification for the model parameters refer to in [[CLAG525X2101C Amendment 10 - Appendix 14.4](#)].

In the dose escalation for the combinations, the dose-toxicity (DLT) relationship is modeled by a 5-parameter BLRM as follows. Let $\pi_1(d_1)$ be the probability of DLT if LAG525 is given as a single agent at Q2W dose d_1 , and $\pi_2(d_2)$ the probability of DLT if PDR001 is given as a single agent at Q2W dose of d_2 . $\pi_{12}(d_1, d_2)$ denotes the probability of DLT if LAG525 is given in combination with PDR001 at Q2W dose d_1 of LAG525 and Q2W dose d_2 of PDR001. The possibility of synergism or antagonism between the safety profiles of the two drugs is captured in the model of odds of DLT rate with combination doses.

$$\text{LAG525: } \text{logit}(\pi_1(d_1)) = \log(\alpha_1) + \beta_1 \log(d_1/d_1^*)$$

$$\text{PDR001: } \text{logit}(\pi_2(d_2)) = \log(\alpha_2) + \beta_2 \log(d_2/d_2^*)$$

$$\text{Odds}(\pi_{12}(d_1, d_2)) = \pi_{12}(d_1, d_2) / (1 - \pi_{12}(d_1, d_2))$$

$$= \exp(\eta(d_1/d_1^*)(d_2/d_2^*)) (\pi_1(d_1) + \pi_2(d_2) - \pi_1(d_1)\pi_2(d_2)) / ((1 - \pi_1(d_1))(1 - \pi_2(d_2))),$$

where $\text{logit}(\pi(d)) = \log[\pi(d) / \{1 - \pi(d)\}]$, $d_1^* = 3 \text{ mg/kg}$ and $d_2^* = 3 \text{ mg/kg}$ are the reference doses of LAG525 and PDR001 respectively, $\alpha_1, \alpha_2, \beta_1, \beta_2 > 0$ and $-\infty < \eta < \infty$.

At the time of each LAG525+PDR001 dose escalation analysis, DLT data up to, and including, the last completed cohort from the single agent dose escalation will be included in the LAG525+PDR001 BLRM. Single agent LAG525 data will be incorporated directly into the BLRM since this data comes from the same study. Single agent PDR001 data from study PDR001X2101 dose escalation will also be utilized. In order to account for between study variability, the DLT data obtained from PDR001X2101 will be down-weighted assuming substantial heterogeneity ([Chen et al 2006](#), [Neuenschwander et al 2010](#)).

The Bayesian approach requires the specification of prior distributions for the model parameters. The prior distributions for the BLRM are derived based on available pre-clinical data on LAG525 and PDR001 and also clinical data for Nivolumab and Pembrolizumab ([Robert et al 2014](#), [Deeks 2014](#)). For further details on the BLRM model including the prior specification for the model parameters, and examples of hypothetical decisions that may be followed during the dose escalation, refer to [[CLAG525X2101C Amendment 10 Appendix 14.3](#)].

After each cohort of patients, the posterior distributions for the probabilities of DLT rates at different dose levels (or combinations) are obtained. Dose recommendation will be based on posterior summaries including the mean, median, standard deviation, 95%-credible interval, and the probability that the true DLT rate for each dose lies in one of the following categories:

- [0, 16%] under-dosing
- [16%, 33%] targeted toxicity
- [33%, 100%] excessive toxicity

Dose recommendation will also be guided by the EWOC principle, which mandates the dose for the next cohort to have less than 25% chance of excessive toxicity. The final estimate of the MTD(s)/ RP2D(s) will also satisfy this condition.

In case of introduction of new dosing schedule during dose-escalation, a separate BLRM will be used. At each dose escalation, the model will be updated and all available information on the dose-DLT relationship from all explored dosing schedules will be used. In order to account for between schedule variability in the assessment of a new dosing schedule, the DLT data obtained from other explored dosing schedules will be down-weighted assuming substantial

heterogeneity. Please see the Appendix 16.1.9 for additional details about the statistical methodology.

All tables and listings will be presented by treatment in which data from different Phase I cohorts treated with the same dose and schedule will be pooled in the CSR.

2.6.2 Phase II part

A Bayesian design will be used in order to estimate Overall Response Rate (ORR) within each group as defined in [Section 2.1](#), and it will be used to provide inferential summaries (e.g., mean, median, interval probabilities) in relation to the patient population.

Each group will enroll approximately 20 patients, and may be extended to 40 patients if at least 3 patients have an objective response for NSCLC, renal cancer, melanoma and mesothelioma and at least 2 patients have an objective response for TNBC.

For a Bayesian design, a prior distribution for the parameter of interest, ORR, must be specified. For the current study, the prior clinical assumption for single agent LAG525 and its combination with PDR001 in the selected patient populations is used in order to derive a minimally informative unimodal Beta prior distribution that reflects the level of uncertainty around ORR before starting the current trial ([Neuenschwander et al 2008](#)). The prior mean ORR is conservatively set to be equal to 20% and the parameters of the minimally informative Beta prior distribution of ORR have been set up as follows:

- $a/(a+b) = 0.2$
- $a = 0.25$
- $b = 1.0$

The primary variable is the Overall Response Rate (ORR), defined as the proportion of patients with a best overall response of complete response (CR) or partial response (PR) based on local Investigator assessment, as defined in RECIST v1.1. Estimation of the true ORR in this part of the study will be based upon the observed ORR for patients in FAS, using a Bayesian analysis.

LAG525+PDR001 combination (groups 6 to 10 and Group 12 to 16): Estimates of the ORR for each group along with mean, median, standard deviation, and 95% credible intervals and the interval probabilities for the true ORR lying within [0%, 20%], [20%, 30%],[30%, 45%], [45%, 60%] and [60%, 100%] will be presented.

If the observed ORR is equal to or greater than 30% for NSCLC or renal cancer or mesothelioma (i.e. ≥ 12 responses (CR or PR) out of 40 patients), 20% for TNBC (i.e. ≥ 8 responses (CR or PR) out of 40 patients) and 45% for melanoma (i.e. ≥ 18 responses (CR or PR) out of 40 patients), then this will be considered as preliminary evidence of antitumor activity of LAG525+PDR001 in the respective patient group.

Note that for a sample size of $n = 40$,

- for NSCLC, mesothelioma and renal cancer, if the observed ORR is 30% then the posterior probability of true ORR greater than 20% is 92.3%.
- for TNBC, if the observed ORR is 20% then the posterior probability of true ORR greater than 10% is 96.6%.

- for melanoma, if the observed ORR is 45% then the posterior probability of true ORR greater than 30% is 97.2%.

2.6.3 Supportive analysis

For the phase II part, the primary analysis on ORR will be repeated using the PPS.

In addition, a Bayesian hierarchical model (BHM) will be applied to the overall response data from patients in the phase II part. Response rates π_j will be inferred for $j = 6, \dots, 16$, for groups 6 to 16 respectively.

For each group j , the number of responders follows a binomial distribution

$$r_j \sim \text{Bin}(n_j, \pi_j)$$

We further let the parameters $\theta_j = \log(\pi_j / (1 - \pi_j))$ be either exchangeable with other indication parameters, or non-exchangeable.

Thus, for each indication j two possibilities arise, with respective probabilities $p_j = (p_{j1}, p_{j2})$, as follows:

1. With probability p_{j1} the parameter θ_j follows a normal distribution with exchangeability parameters μ_1 and τ_1 :

$$\text{i. } \theta_j \sim N(\mu_1, \tau_1^2)$$

2. With probability p_{j2} , θ_j follows a normal distribution with exchangeability parameters $\mu_2 < \mu_1$ and τ_2 :

$$\theta_j \sim N(\mu_2, \tau_2^2)$$

3. With remaining probability $p_{j2} = 1 - p_{j1}$, θ_j follows a weakly-informative prior distribution

$$\theta_j \sim N(m_w, v_w)$$

For the detailed specifications of m_w , v_w , the a-priori weights p_j ($j=1, \dots, J$), and the prior distributions for μ_1 , μ_2 , τ_1 and τ_2 , see [\[CLAG525X2101C Amendment 10 Appendix 14.3\]](#).

At completion of the study, the BHM will be updated with all the data available from the patients in the FAS by disease group. All responses and progressions will be determined as per RECIST 1.1.

LAG525+PDR001 combination (groups 6 to 10 and group 12 to 16): For each of the groups where patients took the recommended combination doses of LAG525+PDR001, estimates of the ORR along with mean, median, standard deviation, and 95% credible intervals and the interval probabilities for the true ORR lying within [0%, 20%], [20%, 30%], [30%, 45%], [45%, 60%] and [60%, 100%] will be presented. Success will be declared for the combo of LAG525 and PDR001 if **both** of the following two criteria are fulfilled:

- a. the true ORR for the indication has posterior mean of at least 30%, and
- b. there is at least 90% posterior probability that the true ORR exceeds 20%.

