  - 2.1 Applying (b) above,  $\tau_1$  and  $\tau_2$  were given a half-normal distribution with scale 0.5, implying a prior 95%-interval for  $\tau$  as (0.016, 1.12), which allows for small to large between-indication heterogeneity ([Spiegelhalter 2004](#)).
  - 2.2  $\mu_1$  and  $\mu_2$  were given normal prior distributions. For  $\mu_1$ , the mean of the prior distribution was set to  $\text{logit}(0.1) = -2.197$  corresponding to no treatment effect. For  $\mu_2$ , the mean was set to  $\text{logit}(0.3) = -0.847$  corresponding to a substantial treatment effect.
  - 2.3 Assume  $\theta_j$  belongs to the first exchangeability distribution. Applying (c) above, the total variance worth approximately one subject is  $3.33^2$ . Since  $\tau_1 \sim \text{HN}(0.5)$  the variance for the normal prior distribution for  $\mu_1$  becomes  $3.296^2$ . The same approach was used to derive the variance for the normal prior distribution for  $\mu_2$ , yielding a variance of  $2.124^2$ .
3. Finally, for each group  $j$ , the **prior mixture weights**  $p_j$  were chosen as
$$p_j = (0.25, 0.25, 0.50), \quad j=1, \dots, 16.$$

This means that each group has 25% prior probability to belong to the first exchangeability distribution, 25% probability to belong to the second exchangeability distribution, and 50% probability to be non-exchangeable with some (or all) of the other indications.

The prior distributions are summarized in [Table 14-21](#), which also shows the prior medians and 95%-intervals for the response rates  $\pi_j$ .

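### SAP 2.6.3 mis-transcribes the supportive hierarchical model (one weight defined twice, plus an ordering that contradicts the priors), so the success rule has more than one reading for borderline counts

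*SAP*

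**What the plan says.** SAP 2.6.3 (Supportive analysis) lets the group log-odds "be either exchangeable with other indication parameters, or non-exchangeable" and states that "two possibilities arise, with respective probabilities" p_j = (p_j1, p_j2). Three numbered components follow:

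- Component 1, weight p_j1: normal with mean mu1 and SD tau1.
- Component 2, weight p_j2: normal with mean mu2 and SD tau2, with mu2 < mu1.
- Component 3, weight again written p_j2, now equal to 1 - p_j1: the log-odds "follows a weakly-informative prior distribution".

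For the weights and priors the SAP refers to Appendix 14.3 of protocol Amendment 10.

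Protocol 10.4.4 has three possibilities with p_j3 = 1 - p_j1 - p_j2, and also states mu2 < mu1. Appendix 14.3.2 says that "each group has 25% prior probability to belong to the first exchangeability distribution, 25% probability to belong to the second exchangeability distribution", with the remaining 50% non-exchangeable. It centres mu1 at logit(0.1), described as "corresponding to no treatment effect", and mu2 at logit(0.3), described as "corresponding to a substantial treatment effect". Table 14-21 summarises the resulting prior for a group response rate as median 0.2 with 95% interval 0.001 to 0.98.

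SAP 2.6.3 declares success for the combination if two conditions hold together: "the true ORR for the indication has posterior mean of at least 30" per cent, and "there is at least 90% posterior probability that the true ORR exceeds 20" per cent.

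**The concern.** The SAP text cannot be programmed as it stands. One symbol carries two meanings, the weights do not sum to one, and a three-element weight vector in the appendix does not fit the SAP's two-element p_j. The ordering is a separate fault, shared by protocol 10.4.4 and the SAP. It makes the second exchangeability distribution the lower one, whereas the appendix makes it the higher one.

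A success declaration is read from this model's posterior. If the programmer has to choose among readings once the responses are known, a group near a cut-off can be called either way, which is what pre-specification is meant to prevent.

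**Working it through.** **Inputs.** All from protocol Appendix 14.3.2 and Table 14-21: mu1 ~ N(-2.197, 3.296²), mu2 ~ N(-0.847, 2.124²), tau1 and tau2 half-normal with scale 0.5, non-exchangeable component N(-1.386, 2.5²), weights 0.25/0.25/0.50. The documents give no response counts, so the counts below are assumptions.

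**1. The plan's own figures.** Total variance is 1/m + 1/(1 - m); subtracting 0.5² = 0.25 leaves the variance of mu.

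- m = 0.1: 11.111 - 0.25 = 10.861, SD 3.296.
- m = 0.3: 4.762 - 0.25 = 4.512, SD 2.124.
- m = 0.2, non-exchangeable: 5 + 1.25 = 6.25, SD 2.5.

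All three agree with the appendix. The three-component mixture at 0.25/0.25/0.50 without ordering has prior median 0.200 and 95% interval 0.0009 to 0.976, which is Table 14-21.

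**2. The SAP weights.** p_j1 + (1 - p_j1) + (1 - p_j1) = 2 - p_j1. At p_j1 = 0.25 this is 0.25 + 0.75 + 0.75 = 1.75. Normalised, the weights are 1/7, 3/7 and 3/7.

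**3. The ordering.** mu2 - mu1 has prior mean -0.847 + 2.197 = 1.350 and SD √(3.296² + 2.124²) = 3.921. So P(mu2 < mu1) = Φ(-1.350/3.921) = 0.365. Enforcing the constraint moves the prior medians to about 63% for mu1 and 12% for mu2, which reverses the no-effect and substantial-effect labels.

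**4. Which reading matches Table 14-21 (stated median 0.2).**

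| Reading | Prior median of ORR |
|---|---|
| Three components, 0.25/0.25/0.50, no ordering | 0.200 |
| Same, mu2 < mu1 enforced | 0.248 |
| Same, mu1 < mu2 enforced | 0.175 |
| SAP weights normalised, 1/7, 3/7, 3/7 | 0.229 |
| Components 1 and 3 only, 0.25/0.75 | 0.176 |
| Components 1 and 3 only, 0.5/0.5 | 0.150 |

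**5. Effect on the success rule.** Hypothetical data: ten groups of 20 with 7, 9, 6, 2, 3, 1, 6, 4, 1 and 1 responders. The posterior comes from grid integration over mu1, tau1, mu2 and tau2; the third decimal moves by about 0.001 with the grid. Results for the 7/20 group:

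| Reading | Posterior mean | P(ORR > 20%) | Success? |
|---|---|---|---|
| Protocol weights, no ordering | 0.322 | 0.910 | yes |
| Protocol weights, mu2 < mu1 | 0.321 | 0.908 | yes |
| SAP weights normalised, no ordering | 0.31 | 0.891 | no |
| SAP weights normalised, mu2 < mu1 | 0.31 | 0.880 | no |
| Components 1 and 3 only, 0.25/0.75 | 0.330 | 0.912 | yes |
| Components 1 and 3 only, 0.5/0.5 | 0.305 | 0.87 | no |

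The posterior-mean criterion can flip too. Take 11/40 with five other groups at 1/20 and four at 16/40. The protocol model gives mean 0.301 and P 0.908 (success); the 0.25/0.75 reading gives 0.286 and 0.882 (no success).

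**6. How often.** Forty simulated trials of ten groups were run per scenario, with extension from 20 to 40 under the protocol's response rule. The true ORRs were all 20%, all 30%, or five groups at 10% and five at 35%. Out of 400 group decisions per scenario, the 0.25/0.75 reading changed 4 to 7 and the 0.5/0.5 reading 1 to 13. Imposing an ordering on the protocol weights changed 0 to 2, with shifts of at most 0.004 in the mean and 0.007 in the probability.

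**The case against.** The best defence is that the intended model can be recovered. The SAP states that it is based on Amendment 10 and sends the reader to Appendix 14.3, where one set of weights sums to one. Protocol 10.4.4 spells out the three components, and only that version without the ordering reproduces Table 14-21. This stands, and it makes the SAP fault a transcription error rather than a missing specification.

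The rival readings are also partly artificial. No document gives 0.5/0.5. The 0.25/0.75 reading discards a component that the SAP writes out, and in the 7/20 example it gives the same decision as the protocol. The normalised weights need a rescaling that the SAP never mentions. The example sits close to the 90% cut and holds every group at 20, although six of the ten have at least 3 responders and could have been extended. All of this limits the size of the effect. It does not make the SAP text a valid model.

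A reader might infer that the ordering contradiction by itself puts the success declarations in doubt. The figures do not support that: under the protocol weights it moves P(ORR > 20%) by less than 0.01.

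The group index (j = 6 to 16, which takes in single-agent group 11) is cosmetic. The SAP states that only the combination part of Phase II would be enrolled, and the same section limits the results to groups 6 to 10 and 12 to 16.

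**Conclusion.** Wrong as written, with a small numerical effect. The SAP's mixture is not a probability model, and the ordering in both documents contradicts the appendix's prior means and, if enforced, its stated prior median (about 0.25 against 0.2). Success under the supportive rule can change with the reading, but only for counts close to a cut-off. The two-component readings changed about 0.3% to 3% of simulated group decisions (1 to 13 of 400). The normalised SAP weights were compared only on hypothetical data sets, so no flip rate is claimed for them.

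A reader might go further and conclude that the trial's evidence of activity depends on this ambiguity. The documents do not support that. Both call the hierarchical model supportive or supporting, while preliminary evidence of activity is judged in SAP 2.6.2 on observed ORR thresholds, which this fault does not touch.

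The sizes rest on the Table 14-21 priors and on assumed response counts and true rates.

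**What to change.** - **SAP 2.6.3:** state three possibilities with p_j = (p_j1, p_j2, p_j3) = (0.25, 0.25, 0.50), and give the third component weight p_j3 = 1 - p_j1 - p_j2. Amend the either/or sentence so that it allows two exchangeability distributions.
- **SAP 2.6.3 and protocol 10.4.4:** delete mu2 < mu1. The unconstrained model reproduces Table 14-21. Simply reversing the sign to mu1 < mu2 does not: it gives a prior of 0.175 (0.0005 to 0.966). If an ordering is wanted, it must agree with the prior means and the Table 14-21 summary must be restated.
- **Tidy-up:** index the SAP groups as 6 to 10 and 12 to 16, and correct j = 1 to 12 in Table 14-21, where the appendix text has 16 groups.

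The cost is a few lines in the SAP and protocol. No data collection or primary analysis changes. The correction should be made before the model is run on the final responses.

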**LAG525+PDR001 combination (groups 6 to 10 and groups 12 to 16):** Estimates of the ORR for each group along with mean, median, standard deviation, and 95% credible intervals and the interval probabilities for the true ORR lying within [0%, 20%], [20%, 30%], [30%, 45%], [45%, 60%] and [60%, 100%] will be presented.

If the observed ORR is equal to or greater than 30% for NSCLC, mesothelioma and renal cancer (i.e.  $\geq 12$  responses (CR or PR) of out 40 patients), 20% for TNBC (i.e.  $\geq 8$  responses [CR or PR] of out 40 patients) and 45% for melanoma (i.e.  $\geq 18$  responses [CR or PR] of out 40 patients), then this will be considered as preliminary evidence of antitumor activity of LAG525+PDR001 in the respective patient group.

Note that for a sample size of  $n = 40$ ,

- for NSCLC, mesothelioma and renal cancer, if the observed ORR is 30% then the posterior probability of true ORR greater than 20% is 92.3%.
- for TNBC, if the observed ORR is 20% then the posterior probability of true ORR greater than 10% is 96.6%.
- for melanoma, if the observed ORR is 45% then the posterior probability of true ORR greater than 30% is 97.2% (See [Section 10.8](#)).

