3. With remaining probability  $p_{j3} = 1 - p_{j1} - p_{j2}$ ,  $\theta_j$  follows a weakly-informative prior distribution

$$\theta_j \sim N(m_w, v_w)$$

For the detailed specifications of  $m_w$ ,  $v_w$ , the a-priori weights  $p_j$  ( $j=1, \dots, J$ ), and the prior distributions for  $\mu_1$ ,  $\tau_1$ ,  $\mu_2$ , and  $\tau_2$ , see [Appendix 14.3.2](#).

At completion of the study, the HM will be updated with all the data available from the patients in the FAS by group. All responses and progressions will be determined as per RECIST v1.1.

**Single-agent LAG525 (groups 1 to 5 and group 11):** For each of the groups where patients take the recommended dose of single agent LAG525, estimates of the ORR along with mean, median, standard deviation, and 95% credible intervals and the interval probabilities for the true ORR lying within [0%, 10%], [10%, 20%], [20%, 30%], [30%, 50%] and 50%, 100%] will be presented.

Success will be declared for the single agent LAG525 if **both** of the following two criteria are fulfilled:

- a. the true ORR for the indication has posterior mean of at least 20%, and
- b. there is at least 90% posterior probability that the true ORR exceeds 10%.

**LAG525+PDR001 combination (groups 6 to 10 and groups 12 to 16):** For each of the groups where patients take the recommended combination doses of LAG525+PDR001, estimates of the ORR along with mean, median, standard deviation, and 95% credible intervals and the interval probabilities for the true ORR lying within [0%, 20%], [20%, 30%], [30%, 45%], [45%, 60%] and [60%, 100%] will be presented.

Success will be declared for the combo of LAG525 and PDR001 if **both** of the following two criteria are fulfilled:

- a. the true ORR for the indication has posterior mean of at least 30%, and
- b. there is at least 90% posterior probability that the true ORR exceeds 20%.

Additional supportive [REDACTED] analyses will be conducted to support the primary objective, if appropriate, and the details of these analyses will be defined in the RAP.

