**Combination LAG525+PDR001 (groups 6 to 10 and groups 12 to 16):**

Assume that efficacy will be claimed for the combination of LAG525 + PDR001 if observing an ORR of  $\geq 30\%$  for NSCLC or renal cancer or mesothelioma,  $\geq 20\%$  for TNBC and  $\geq 45\%$  for melanoma, the operating characteristics of the design are provided in [Table 10-3](#) and [Table 10-4](#), including the probability of stopping the enrollment at 20 patients (fewer than 3 responses in the first 20 patients for NSCLC, renal cancer, melanoma and mesothelioma and fewer than 2 responses in the first 20 patients for TNBC), and the probabilities to extend the enrollment to 40 patients and observe an ORR  $\geq 30\%$  (for NSCLC, renal cancer, mesothelioma), 20% (for TNBC) and  $\geq 45\%$  (for melanoma).

Specifically,

- If the true ORR is 15% for NSCLC, mesothelioma or renal cancer (i.e. in the unacceptable efficacy range), the probability of observing an ORR  $\geq 30\%$  is 1.2% (< 5%).
- If the true ORR is 30% for melanoma (i.e. in the unacceptable efficacy range), the probability of observing an ORR  $\geq 45\%$  is 3.2% (< 5%).
- If the true ORR is 40% for NSCLC, mesothelioma or renal cancer (i.e. in the clinically significant efficacy range), the probability of observing an ORR  $\geq 30\%$  is 92.8%.
- If the true ORR is 55% for melanoma (i.e. in the clinically significant efficacy range), the probability of observing an ORR  $\geq 45\%$  is 92.3%.
- If the true ORR is 10% for TNBC (i.e. in the unacceptable efficacy range), the probability of observing an ORR  $\geq 20\%$  is 4.1% (< 5%).
- If the true ORR is 30% for TNBC (i.e. in the clinically significant efficacy range), the probability of observing an ORR  $\geq 20\%$  is 94.2%.

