### 14.3.2 Prior specifications for phase II hierarchical model

As a supporting analysis, for patients in phase II part, the ORR for each of 16 groups is estimated using a hierarchical model with two exchangeable groups and one non-exchangeable group (see [Section 10.4.4](#)) and data from all 16 groups.

The model is given in [Section 10.4.4](#) and the details of prior specifications are provided here. Three results will be used in the below specifications:

- For a probability  $\pi$ , we construct a weakly-informative prior distribution on the logit-scale, i.e. for  $\log(\pi/(1-\pi))$ , as follows: the prior median is set to a plausible value  $m_\pi$ , and the “prior sample size” will be approximately one. For the latter, under a normal approximation, the resulting variance on the logit-scale is  $v_\pi = 1/m_\pi + 1/(1 - m_\pi)$ . This leads to a weakly-informative normal prior distribution for  $\log(\pi/(1-\pi))$  with mean  $m_\pi$  and variance  $v_\pi$ .
- For exchangeable group-specific parameters  $\theta_j = \log(\pi_j/(1-\pi_j))$ ,  $\theta_j \sim N(\mu, \tau^2)$ , let the prior distributions be  $\mu \sim N(m_\mu, v_\mu)$  and  $\tau \sim HN(s)$ . Here,  $HN(s)$  denotes the half-normal distribution with scale parameter  $s$ .

- c. Assume that the marginal (total) variance  $V(\theta)$  as well as the scale parameter  $s$  are known, where the first defines the a-priori uncertainty for the indication parameters, and the second defines the a-priori degree of borrowing across groups. From these specifications, the prior variance of  $\mu$  follows from the law of total variance

$$V(\theta) = E(V(\theta|\mu,\tau)) + V(E(\theta|\mu,\tau)) = E(\tau^2) + V(\mu) = s^2 + v_\mu.$$

From this, the variance of  $\mu$  is  $v_\mu = V(\theta) - s^2$ . Based on these results, we specified the prior distributions for parameters in the hierarchical model as follows:

1. The group-specific normal priors for the **non-exchangeable** case, defined by  $m_w$  and  $v_w$  were derived from (a) above. The prior median for the response probability was set as 0.2 (a limited treatment effect), and the corresponding variance was derived as described in (a) above. This results in

$$m_w = \text{logit}(0.2) = -1.386, \quad v_w = 1/0.2 + 1/(1 - 0.2) = 2.5^2$$

2. For the **exchangeable** cases, the specifications were as follows:

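### The supportive hierarchical model applies one 30%/20% success bar to all ten combination groups, although the plan's own rates differ for melanoma (45%) and TNBC (20%)

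*SAP*

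**What the plan says.** The supportive rule is the same in SAP 2.6.3 and Protocol 10.4.4. For groups 6 to 10 and 12 to 16, success requires that "the true ORR for the indication has posterior mean of at least 30" percent and that "there is at least 90% posterior probability that the true ORR exceeds 20" percent. Neither document makes an exception for melanoma (groups 7 and 10) or TNBC (groups 14 and 16). Protocol 14.3.2 gives the model's status: "As a supporting analysis, for patients in phase II part".

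The primary rule is disease-specific. SAP 2.6.2 begins "If the observed ORR is equal to or greater than 30% for NSCLC or renal cancer or mesothelioma" and goes on to 20% (8 of 40) for TNBC and 45% (18 of 40) for melanoma. Protocol 10.4.2 sets the same bars and attaches the consequence: "then this will be considered as preliminary evidence of antitumor activity of LAG525+PDR001 in the respective patient group". It also explains the lower TNBC extension threshold by a lower target ORR.

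Protocol 10.8 gives opposite readings of the same true rate: "If the true ORR is 30% for melanoma (i.e. in the unacceptable efficacy range") and "If the true ORR is 30% for TNBC (i.e. in the clinically significant efficacy range").

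The protocol's single-agent rule has the same pattern ("the true ORR for the indication has posterior mean of at least 20" percent, with 90% probability of exceeding 10%, for every disease). SAP 1.1 records that only the combination part of Phase II would be enrolled, so that rule has no practical effect.

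**The concern.** A supportive analysis should ask the same question as the primary one by a different method. Here, four of the ten groups are asked a different question. A melanoma group whose posterior mean equals the rate the protocol calls unacceptable satisfies the first criterion. A TNBC group at its stated target of 20% fails it. Neither document gives a reason for a common bar or says which conclusion prevails when the two differ.

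What is at stake is the wording of the report. It could announce success in melanoma where the primary bar was missed, or withhold it in TNBC where the primary bar was met. Extension from 20 to 40 patients depends on responder counts, so enrolment is not affected.

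**Working it through.** **Inputs.** Prior Beta(0.25, 1) (Protocol 10.4.2, SAP 2.6.2); primary bars of 18/40 and 8/40; extension at 3 or more responders in 20, or 2 or more for TNBC (Protocol 10.7, SAP 2.12); hierarchical priors from Protocol 14.3.2.

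**Formulas.** With r responders in n, the posterior is Beta(0.25 + r, 1 + n − r), with mean (0.25 + r)/(1.25 + n). The two-stage pass probability at true rate p, extension threshold g and bar R is the sum over x = g to 20 of P(X = x) × P(Y ≥ R − x), where X and Y are independent Bin(20, p).

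**Reproducing the plan's figures.** P(ORR > 30% | 18/40) = 97.2%; P(ORR > 10% | 8/40) = 96.6%; P(ORR > 20% | 12/40) = 92.3%. Melanoma passes its bar 3.2% of the time at a true 30% and 92.3% at 55%. TNBC passes 4.1% at 10% and 94.2% at 30%. All match Protocol 10.4.2 and 10.8.

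**Common rule as a responder count, n = 40.**
- 12/40: mean 12.25/41.25 = 29.7%, which fails the first criterion.
- 13/40: mean 13.25/41.25 = 32.1%, P(ORR > 20%) = 96.2%, which passes.
- The model's non-exchangeable component, logit ORR ~ N(−1.386, 2.5²), gives means of 29.8% and 32.3%, so the same count.

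Group alone, melanoma at 13–17/40 is therefore a success that misses its primary bar, and TNBC at 8–12/40 meets its primary bar without success (8/40: mean 20.0%, P(ORR > 20%) = 46.9%).

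**Two-stage pass probabilities, group alone.** The two bars are nested, so disagreement is the difference between them.

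| Group | True ORR | Common rule | Own primary bar | Disagreement |
|---|---|---|---|---|
| Melanoma | 20% | 4.3% | <0.1% | 4.3% |
| Melanoma | 30% | 42.2% | 3.2% | 39.0% |
| Melanoma | 40% | 87.1% | 31.1% | 56.0% |
| Melanoma | 55% | 99.9% | 92.3% | 7.5% |
| TNBC | 10% | <0.1% | 4.1% | 4.1% |
| TNBC | 20% | 4.3% | 55.7% | 51.4% |
| TNBC | 30% | 42.3% | 94.2% | 51.9% |
| TNBC | 40% | 87.1% | 99.8% | 12.6% |

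**Groups that stop short of 40.** The Amendment 10 study status counts 235 expansion patients (its total of 450 less 255 gives 195). Since 235/40 = 5.9 and 195/40 = 4.9, at most five or four of the ten groups could then have reached 40. At n = 20 the common rule needs 7/20 (mean 34.1%, P(ORR > 20%) = 92.7%). Reading the percentage bars as 9/20 and 4/20, which is an assumption, a true 30% gives melanoma 39.2% against 11.3% and TNBC 39.2% against 89.3%. At every n from 20 to 40 the common rule sits 2–6 responders below the melanoma bar and 2–5 above the TNBC bar, but only 0–1 above the bar for the other three diseases.

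**Borrowing.** A simulation of the ten-group model with the appendix priors (no ordering of the two means, 1,000 trials per scenario, standard error up to about 1.6 points) assumed NSCLC, renal and mesothelioma at either 15% or 40%. Melanoma at 30% then passes 36% or 63% if extended, and 28% or 55% at n = 20. TNBC at 30% passes 35% or 62%, and 31% or 57%. These figures are illustrative only.

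**The case against.** The strongest reply is that the rule is labelled supportive in both documents, triggers no action, and uses a posterior mean and a tail probability rather than an observed rate, so some disagreement is expected. That is partly right. Even where the bar fits, 12/40 in NSCLC, renal cancer or mesothelioma meets the primary bar and fails the mean; under the two-stage design this happens 13.6% of the time at a true 30% and 5.7% at 40%. But that is a one-responder difference of scale, whereas the melanoma and TNBC gaps come from the thresholds themselves.

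It is also fair that the exact figures above ignore borrowing, which the rule's own model includes. The size therefore depends on the other groups' results. The stated thresholds do not.

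Per-group summaries offer partial protection. The interval probabilities let a reader recover P(ORR > 30%) for melanoma. They do not give P(ORR > 10%) for TNBC, because the lowest cut is 20%, although the lower limits of the 95% credible interval and of the exact 90% confidence interval can be compared with 10%.

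Finally, changing thresholds late in an open-label study with quarterly ORR review (Protocol 8.5) invites criticism, and a single precedence sentence would remove much of the risk. That sentence belongs in the fix, but alone it would leave in place a success label that contradicts the protocol's own rates.

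**Conclusion.** The concern holds. The common bar is too lenient for melanoma and too strict for TNBC by the plan's own definitions, in both documents and without a stated reason. Group alone, with extension whenever the responder threshold is met (permitted, not required), a true 30% passes as success 42.2% of the time in melanoma against 3.2% under its own bar, and 42.3% in TNBC against 94.2%. The direction is the same at every n from 20 to 40; the exact size under borrowing is uncertain. The consequence is limited to a potentially misleading supportive statement for groups 7, 10, 14 and 16. It should be fixed, but it does not touch the primary result.

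**What to change.** In Protocol 10.4.4 and SAP 2.6.3, make the rule disease-specific with the protocol's existing rates:
- Melanoma: posterior mean ≥45% and P(ORR > 30%) ≥90%.
- TNBC: posterior mean ≥20% and P(ORR > 10%) ≥90%.
- NSCLC, renal cancer, mesothelioma: unchanged.

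State that the primary bar governs if the two differ. Record that the rates come unchanged from Protocol 10.4.2 and 10.8, and report the existing rule's result alongside, to answer any charge of a data-driven change.

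**What it does not achieve.** Agreement is not exact. Group alone, for n from 20 to 40, the melanoma rule is 0–1 responder stricter than its primary bar (10/20 against 9/20; 19/40 against 18/40). The TNBC rule equals its bar from n = 21 to 40 but needs 5/20 rather than 4/20 at n = 20, where 4/20 gives P(ORR > 10%) = 89.4%. Melanoma at a true 55% passes 86.7% against 92.3%, so disagreement falls from 7.5% to 5.6% with extension but rises from 10.9% to 11.9% at n = 20. In the illustrative borrowing run with the other diseases at 40%, it rises from 8.5% to 11.1%. TNBC at n = 20 and a true 30% passes 76.2% against 89.3%, and disagreement falls from 50.1% to 13.0%.

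**Separate drafting corrections for the same amendment.** SAP 2.6.3 announces two components, lists three and uses p_j2 twice; it should state three, with the appendix weights (0.25, 0.25, 0.50). Its index 6 to 16 takes in the unenrolled single-agent group 11; use 6–10 and 12–16. Table 14-21 runs to 12 where the text of Protocol 14.3.2 runs to 16. Both documents require μ2 < μ1, yet the appendix centres μ1 at logit(0.1) and μ2 at logit(0.3); these must be reconciled.

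**Cost.** No patients and no new data; a few lines of model code, a written and approved protocol amendment (Protocol 12.1), and a SAP amendment before database lock or an addendum after it (SAP section 1).
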